10.2.5. Treatment Week 4 (Visit T2; Day 29 ±3 days)

If the patient is withdrawing early from the study at this visit, proceed to [Section 10.3](#) for the list of the required assessments.

If the patient is withdrawing from IMP treatment at this visit, proceed to [Section 10.3.1](#) for the list of the required assessments. The patient will be asked to continue to be followed using the protocol-specified visit schedule.

Patients refusing to continue to return to the clinic for protocol assessments after withdrawing from IMP treatment will be asked to participate in phone calls from the site at protocol-specified visits, or at a minimum at 12 weeks, to inquire about the patient's current health status and collect information on AEs (eg, recent procedures, hospitalizations, and if the patient has died, the cause of death). If the patient consents for telephone contacts, schedule the next protocol-specified visit.

Patients will undergo the following assessments and procedures at Visit T2:

- Concomitant and prohibited medication review (ongoing)
- Assess AEs, SAEs, and potential clinical endpoints
- Vital signs
- Clinical safety laboratory evaluations (hematology, blood chemistry, and urinalysis)
- Basic fasting lipids (TC, calculated LDL-C, HDL-C, non-HDL-C, and TG)
- PK sample prior to dose
- Conduct diet and exercise counseling
- Record unused IMP and ezetimibe and reissue study drug bottles
- Schedule next visit

10.2.6. Treatment Week 8 (Visit T3; Day 57 ±3 days)

If the patient is withdrawing early from the study at this visit, proceed to [Section 10.3](#) for the list of the required assessments.

If the patient is withdrawing from IMP treatment at this visit, proceed to [Section 10.3.1](#) for the list of the required assessments. The patient will be asked to continue to be followed using the protocol-specified visit schedule.

Patients refusing to continue to return to the clinic for safety assessments after withdrawing from IMP treatment will be asked to participate in phone calls from the site at protocol-specified visits, or at a minimum at 12 weeks, to inquire about the patient's current health status and collect information on AEs (eg, recent procedures, hospitalizations, and if the patient has died, the cause of death). If the patient consents for telephone contacts, schedule the next protocol-specified visit.

Patients will undergo the following assessments and procedures at Visit T3:

- Concomitant and prohibited medication review (ongoing)
- Assess AEs, SAEs, and potential clinical endpoints
- Vital signs
- Clinical safety laboratory evaluations (hematology, blood chemistry, and urinalysis)
- Basic fasting lipids (TC, calculated LDL-C, HDL-C, non-HDL-C, and TG)
- PK sample prior to dose
- Conduct diet and exercise counseling
- Record unused study drug and reissue IMP and ezetimibe bottles
- Schedule next visit

10.2.7. Treatment Week 12/EOS (Visit T4; Day 85 ±3 days)

Patients will undergo the following assessments and procedures at Week 12 (Visit T4) when completing an EOS visit or withdrawing from study (early withdrawal).

Patients will undergo the following assessments and procedures at Visit T4:

- Concomitant and prohibited medication review (ongoing)
- Assess AEs, SAEs and potential clinical endpoints
- Physical Exam
- Weight (kg)
- 12-lead ECG
- Vital Signs
- Clinical safety laboratory evaluations (hematology, blood chemistry, and urinalysis)
- Basic fasting lipids (TC, calculated LDL-C, HDL-C, non-HDL-C, and TG)
- Special fasting lipids and other biomarkers (including apoB and hs-CRP)
- HbA_{1C}
- PK sample prior to dose
- Conduct diet and exercise counseling
- Drug return and recording of drug compliance

- Complete study status in IWRS (ie, early withdrawal or completed study).

10.3. Subject Withdrawal Criteria

10.3.1. Early Withdrawal from the Study

Patients must remain in the study until the last scheduled visit at Week 12 (Visit T4) to be considered as having completed participation in the study.

Patients who withdraw from IMP and/or ezetimibe prior to Week 12 (Visit T4) for any reason will be asked to continue to be followed for safety assessments, including basic fasting lipids, at clinic visit following the protocol-specified visit schedule (see [Appendix 1](#)).

Patients who temporarily withdraw from IMP and/or ezetimibe prior to Week 12 (Visit T4) for any reason may restart IMP and/or ezetimibe providing that (1) the patient and the investigator are in agreement regarding this course of action, (2) the patient has been off of IMP for 4 weeks or less; and (3) IMP can be started as soon as possible. For cases where the patient has been off of IMP for more than 4 weeks, the investigator must contact the medical monitor for approval prior to restarting IMP.

Patients who refuse to continue to return to the clinic for safety assessments will be asked to participate in phone calls from the site at protocol-specified visits (see [Appendix 1](#)), or at a minimum at 12 weeks, to collect information on AEs, concomitant medications, and current health status.

The patient's decision to participate in the clinical study is voluntary. Patients may refuse to continue in the study and/or withdraw from participation in this study at any time, for any reason, specified or unspecified, and without penalty or loss of benefits to which the patient is otherwise entitled.

It is the right and duty of the investigator to interrupt the treatment of any patient whose health or well-being may be threatened by continuation in this study. Such patients should be withdrawn from the study and should not be continued under a modified regimen.

Patients who are withdrawn from the study may not re-enter. The reasons for withdrawal from this study may include:

- Patient's withdrawal of consent
- Failure to comply with the protocol
- Lost to follow-up
- Illness, condition, or procedural complication (including AEs) affecting the patient's ability to participate or requiring prohibited medication
- The Sponsor or investigator terminates the study
- In the investigator's judgment, it is deemed in the best interest of the patient to discontinue his/her participation in the study
- Any other reason

If a patient is lost to follow-up, every reasonable effort must be made by the clinical site personnel to contact the patient and determine the reason for discontinuation/withdrawal. The measures taken to follow-up must be documented.

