11.2.6. Monitoring and Follow-up of Adverse Events

Patients having AEs will be monitored with relevant clinical assessments and laboratory tests, as determined by the investigator. All follow-up results are to be reported to the Sponsor personnel or the authorized Medical Monitor. Any actions taken and follow up results must be recorded either on the appropriate page of the eCRF or in appropriate follow-up written correspondence, as well as in the patient's source documentation. Follow-up laboratory results should be filed with the patient's source documentation.

For all AEs that require the patient to be discontinued from the study, relevant clinical assessments and laboratory tests must be repeated at appropriate intervals until final resolution, stabilization of the event(s), or until the patient is lost to follow-up or dies.

Patients with AEs that are ongoing at study completion or study withdrawal must be followed until resolution or for 30 days after the last study visit, whichever comes first (see [Section 11.3](#)).

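### Section 10.3.1 keeps patients who stop study drug in follow-up, but its safety-interruption sentence, read literally, withdraws them from the study and loses obtainable Week 12 values

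*Protocol*

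**What the plan says.** Protocol Section 10.3.1 contains two instructions that can reach the same patient.

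- **Stay in follow-up.** "Patients who withdraw from IMP and/or ezetimibe prior to Week 12 (Visit T4) for any reason will be asked to continue to be followed" at clinic visits on the normal schedule, with basic fasting lipids. A temporary stop, again whatever its cause, may be followed by a restart if patient and investigator agree. The medical monitor's approval is needed after more than 4 weeks off drug.
- **Leave the study.** The investigator is to interrupt the treatment of "any patient whose health or well-being may be threatened by continuation in this study". The next sentence reads "Such patients should be withdrawn from the study and should not be continued under a modified regimen", and the one after it "Patients who are withdrawn from the study may not re-enter".

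Other sections follow the first instruction. The Week 4 visit (10.2.5) has separate branches for leaving the study and for leaving study drug. In the second branch, "The patient will be asked to continue to be followed using the protocol-specified visit schedule". Week 8 (10.2.6) says the same. The laboratory rules for liver tests, creatinine, hemoglobin, CK and triglycerides (11.1.6.3.1 to 11.1.6.3.4 and 11.1.6.3.6) ask patients taken off study drug to stay on the visit schedule. The liver rule allows interruption with rechallenge, and the CK rule allows a hold with resumption.

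Sections 12.3 and 12.5 define the primary analysis on all randomized patients, with multiple imputation that depends on whether the patient is still on treatment. An observed-data analysis is confirmatory.

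**The concern.** A treatment interruption by the investigator for safety is one of the reasons for stopping study drug that the first instruction covers. A site therefore finds two outcomes for one patient in a single section: continued visits with a possible restart, or final removal from the study. Which applies depends on the sentence the site acts on.

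The practical exposure is mainly clinical adverse events. Defined laboratory abnormalities have their own explicit rules.

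A patient removed from the study before Week 12 gives a discontinuation sample but no Week 12 LDL-C. Week 12 apoB and hs-CRP go as well. Both are in the step-down sequence and are scheduled only at Day 1 and Week 12 (11.7.1, Appendix 1). Week 12 TG and HDL-C are also lost, and Section 12.6 analyses those on observed data only. The loss follows harm, so it may be informative. It falls on the off-drug patients whose actual values an all-randomized analysis most needs.

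**Working it through.** **Reading the text.** The trigger in the second instruction refers to continuing in the study, which could mean that participation itself is the hazard. But the action it describes is interrupting treatment, the consequence is withdrawal from the study, and no exception is made for off-drug follow-up. The literal reading is therefore available to a site.

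**The plan's own figure.** Section 12.2 gives 150 vs 75 patients, a difference of 15 points, SD 15, two-sided 5%, and power above 95%. Recomputed power is 0.9999998 by both the normal approximation and the noncentral t. About 40 vs 20 patients would already give 95%.

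**Effect on power.** If 15% of the active arm is off drug with no remaining effect, the all-randomized difference is 15 × 0.85 = 12.75. With 144 vs 75 patients observed, power is 0.99997 at SD 15. It is 0.9999 at SD 15.93, which adds the mixing of on- and off-drug patients: 15 × √(1 + 0.15 × 0.85) = 15.93.

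**Effect on the observed-data confirmatory analysis.** The protocol gives no rate for safety stops or for how many would leave the study, so these are assumptions:

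- p = share of the active arm stopped for safety: 5%, 10% or 15%
- f = share of those withdrawn from the study: 0.25
- r = share of those withdrawn who would otherwise have attended Week 12: 0.5, since the protocol expects some off-drug patients to accept only phone calls
- off-drug LDL-C returns to the placebo level, and there is no such loss on placebo

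Formulas:

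- All-randomized difference: 15(1 − p)
- Observed-data difference: 15(1 − p)/(1 − pf)
- Observed-data difference if the share r had stayed: 15(1 − p)/(1 − pf(1 − r))
- Planned SE: 15 × √(1/150 + 1/75) = 2.12

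| p | All-randomized | Observed data | Overstatement (in SE) | Part due to the instruction (in SE) | Withdrawn, 150pf | Recoverable values, 150pfr |
|---|---|---|---|---|---|---|
| 5% | 14.25 | 14.43 | 0.18 (0.09) | 0.09 (0.04) | 1.9 | 0.9 |
| 10% | 13.50 | 13.85 | 0.35 (0.16) | 0.18 (0.08) | 3.8 | 1.9 |
| 15% | 12.75 | 13.25 | 0.50 (0.23) | 0.25 (0.12) | 5.6 | 2.8 |

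Example at p = 10%: 13.5/0.975 = 13.846 and 13.5/0.9875 = 13.671, so the part due to the instruction is 0.175 points.

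**Outer bound.** If every safety stop were lost (f = 1), the overstatement would be 15p = 0.75, 1.50 or 2.25 points. This is not a realistic case, because the laboratory rules keep their patients in follow-up.

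**The case against.** The strongest reply is that the two instructions have different triggers: one covers stopping the drug, the other covers danger from being in the study, for which ending participation is the right response. That reading is reasonable, and many sites may adopt it. It does not settle the matter, because the sentence starts from interrupting treatment and does not say that off-drug follow-up remains open.

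Several other replies stand and limit the point:

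- **Laboratory rules.** A reader might infer that the sentence overrides Section 11.1.6.3. It would not in practice. Those rules are specific to defined events, and sites would apply them over a general clause.
- **Other withdrawal text.** A reader might see the same fault in the list of withdrawal reasons, which includes "Illness, condition, or procedural complication (including AEs) affecting" the ability to participate and the investigator's judgment that "it is deemed in the best interest of the patient to discontinue his/her participation in the study", or in Section 11.2.6, which begins "For all AEs that require the patient to be discontinued from the study". These passages only recognise that study withdrawal can happen. None of them orders it when drug is stopped.
- **Partial data.** Sections 10.2.7 and 10.3.2 call for the final-visit assessments at early withdrawal, so LDL-C, apoB and hs-CRP are sampled, only earlier than Week 12. How such samples enter the analysis may be set in the SAP, which is not shown.
- **Safeguards.** Section 10.3.2 requires written notice of a withdrawal within 48 hours and urges that visits be completed, so a site that over-applies the sentence can be corrected for later patients. Adverse event follow-up also continues after withdrawal.
- **Assumed inputs.** Nothing in the protocol supports particular values of p, f or r.

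**Conclusion.** The inconsistency is real and is in current text, but its effect is small. Under the stated assumptions it costs about 1 to 3 recoverable Week 12 values among 150 active-arm patients and shifts the observed-data confirmatory analysis by 0.09 to 0.25 points (0.04 to 0.12 SE). The figures scale with the assumed rates.

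A reader might go further and infer that the primary result or its power is at risk. The documents do not support that. Power stays above 99.9%. The primary and step-down endpoints are multiply imputed according to treatment status, and no bias in that analysis has been shown. What remains is a somewhat greater reliance on imputation for patients stopped for harm. It is worth removing because it is avoidable and cheap to avoid.

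**What to change.** Replace the one sentence in Section 10.3.1 with:

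*Such patients should have IMP interrupted or be withdrawn from IMP and asked to continue the scheduled visits through Week 12, including lipids, apoB and hs-CRP; they should be withdrawn from the study only if consent is withdrawn or the investigator judges that continued participation itself is not in the patient's interest.*

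Leave the list of withdrawal reasons and Section 11.2.6 unchanged. Narrowing them would cut into the investigator's discretion to protect a patient, which is more than the problem needs. The bar on re-entry can also stay, since it would then apply only to patients who have truly left the study.

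The cost is a minor amendment and a site memo. No visits or samples are added, because all of them are already in Appendix 1.

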10.3.2. Procedures for Early Withdrawal

If a patient withdraws or is removed from the study for any reason, the patient should complete an End of Study visit. Reason for withdrawal, date of the discontinuation, and date of the last dose of study drug should be recorded in the appropriate section of the eCRF. Additionally, the discontinuation visit date must be registered in IWRS. Study drug assigned to the withdrawn patient may not be assigned to another patient.

All effort should be made to have each patient complete all study visits on schedule according to the protocol. Accommodations for early or late visits in special circumstances will be considered by the Sponsor to prevent early withdrawal. Written notice (regardless of cause) is to be provided within 48 hours of the withdrawal to the Sponsor personnel or the Medical Monitor. At the time of discontinuation, every effort should be made to ensure all relevant procedures and evaluations scheduled for the final study visit are performed. Except in the case of a medical emergency, the procedures and assessments detailed in [Section 10.3](#) will be performed upon the discontinuation of the study.

11. ASSESSMENT OF SAFETY

11.1. Safety Parameters

At all clinic visits, investigators will review all safety information including vital signs, AEs, concomitant medications, and ECG reports and will ensure that the collected data are recorded into the appropriate eCRF. Additionally, clinical laboratory samples will be collected and sent for analysis and the investigator will review the results to ensure continued patient safety while participating in the study.

11.1.1. Demographic/Medical History

Demographic data and a complete medical history will be obtained from the patient. For medical history, conditions that are relevant and/or clinically significant should be captured with at least a start date (month and year) and whether the condition is ongoing or resolved. All surgeries regardless of date should be reported.

11.1.2. Vital Signs

Vital signs will include diastolic and systolic blood pressure as well as heart rate.

The patient should sit quietly for 5 minutes prior to collection of vital signs. At all time points, vitals will be collected prior to blood collection. Blood pressure and heart rate will be measured using a calibrated, fully automated machine with a cuff that is appropriate to the size of the upper arm. If a fully automated machine is not available, blood pressure may be measured manually. The same method (either automated or manual) and the same arm (right or left) must be used throughout the study. The patient should be in a seated position with feet touching the floor. Patients should be seated quietly for at least 5 minutes in a chair with their backs supported, their feet flat on the ground, and their arms bared and supported at heart level.

11.1.3. Weight, Height, and Body Mass Index

Body weight will be measured in the morning using consistent scales while the patient is fasting, after voiding, and without shoes and outerwear (eg, coats).

Height will be measured using standard clinic procedures.

BMI will be calculated using the formula:

$$\text{BMI (kg/m}^2\text{)} = \text{weight in kg} / (\text{height in meters})^2$$

11.1.4. Physical Examination

Physical examinations (PE) will include an assessment of the following:

- General appearance
- Skin
- Eyes, ears, nose, and throat
- Head and neck

- Extremities
- Musculoskeletal examination
- Respiratory examination
- Cardiovascular assessment, including rhythm and presence of cardiac abnormalities
- Abdominal examination
- Neurologic examination including documentation of the presence of abnormalities in mental status and motor and sensory function
- Any additional assessments necessary to establish baseline status or evaluate symptoms or adverse experiences

Documentation of the PE findings will be included in the source documentation at the clinical site. Significant findings prior to the start of study drug will be recorded on the Medical History/Current Medical Conditions page of the eCRF. Only changes from baseline physical examination findings that meet the definition of an AE will be recorded on the AE page of the eCRF.

Note: Additional information will be collected regarding muscle-related AEs. See [Section 12.7.2](#).

11.1.5. Electrocardiogram

ECG collection will be preceded by a 10-minute rest time during which the patient will remain in the supine position. At each time point, ECGs will be collected prior to blood collection. ECGs will be assessed using machine readings and physician review.

11.1.5.1. Monitoring and Management of Abnormal Electrocardiograms

If a clinically significant ECG abnormality not present at baseline (screening) is determined by the investigator to be related to study drug, the abnormality will be discussed with the Sponsor personnel or the authorized Medical Monitor. The event will be followed and evaluated with additional tests (if necessary) until the underlying cause is determined or the event is brought to an acceptable resolution. Additional clinical and laboratory information will be collected and carefully documented in order to better characterize the ECG abnormality and rule out alternative causes. ECG findings determined to be a clinically significant change from baseline should be reported as an AE regardless of causality.

Unscheduled ECG assessments will be completed at the discretion of the investigator.

11.1.6. Clinical Laboratory Tests

11.1.6.1. Laboratory Parameters (Safety)

Patients will be in a seated position during the blood collection. Clinical laboratory parameters and tests will include those listed in [Table 3](#). Collection schedule, schedule of laboratory parameters by visit, and instructions are in the Clinical Laboratory Manual provided by the Central Laboratory.

Table 3: Clinical Laboratory Parameters (Safety)

Clinical Laboratory Test	Clinical Laboratory Test
Hematology 
• Hematocrit (Hct)• Hemoglobin (Hgb)• Mean corpuscular hemoglobin (MCH)• Mean corpuscular hemoglobin concentration (MCHC)• Mean corpuscular volume (MCV)• Platelet count• Red blood (RBC) cell count• White blood (WBC) cell count with differential (absolute and %)	Blood Chemistry (serum, fasting) 
• Albumin (Alb)• Alkaline phosphatase (ALK-P)• Alanine aminotransferase (ALT; serum glutamic pyruvic transaminase [SGPT])• Aspartate aminotransferase (AST; serum glutamic oxaloacetic transaminase [SGOT])• Blood urea nitrogen (BUN)• Calcium (Ca)• Carbon dioxide (CO₂)• Chloride (Cl)• Creatinine• Creatine kinase (CK)• Glucose• Lactate dehydrogenase (LDH)• Phosphorus• Potassium (K)• Sodium (Na)• Total bilirubin (TB)^a• Total protein• Uric acid
Urinalysis (Dipstick) 
• Clarity• Bilirubin• Color• Glucose• Ketones• Leukocyte esterase• Nitrite• Occult blood• pH• Protein• Specific gravity• Urobilinogen	

Table 3: Clinical Laboratory Parameters (Safety) (Continued)

Clinical Laboratory Test	Clinical Laboratory Test
Urinalysis (Microscopic)-only if urine dipstick abnormal 
 • Bacteria • Casts • Crystals • Epithelial cells • RBC • WBC 	Coagulation (screening for all patients, T1 and 3-5 days after T1 in patients receiving anticoagulation therapy, only) 
 • Prothrombin time (PT) • International normalized ratio (INR)
Other Screening Labs 
 • Hepatitis B surface antigen (HBsAg) • Hepatitis C virus (HCV)^b • Serum pregnancy test (only for females of childbearing potential) • Follicle-stimulating hormone (FSH; Females <55 years and >1 year without menses) • Urine pregnancy test prior to randomization (for female of child bearing potential) • Thyroid-stimulating hormone (TSH) 	Additional samples 
 • Hemoglobin A_{1C} (HbA_{1C})

^a If TB $\geq 1.2 \times$ ULN, a reflex indirect (unconjugated) bilirubin will be obtained.

^b If hepatitis C antibody (HCV-AB) is positive, a reflex HCV RNA will be performed to rule out active disease.

